5.1.2 Treatments

Management of and dose modifications in response to adverse events related to study medications are outlined in section 7.7, below.

5.1.2.1 Cohort A:

Tremelimumab

Tremelimumab is a human IgG2 anti-CTLA-4 mAb. It will be given at a dose of 75 mg IV over 1 hour in an outpatient setting beginning week 1 of the trial. No premedications are needed. This drug will only be used as neo-adjuvant therapy. In the post-resection portion of the study, Cohort A will only receive Durvalumab according to its schedule (see tables 10.1, 10.2, 10.3). Pharmaceutical details and preparation are given in section 8.

Durvalumab

Durvalumab, a human IgG1κ mAb directed against PD-L1, and with reduced binding to C1q and the Fcy receptors. It will be given immediately following tremelimumab beginning week 1 at a dose of 1500 mg IV over 1 hour. No premedications are needed. Pharmaceutical details and preparation are given in section 8.

5.1.2.2 Cohort B

Oleclumab

Oleclumab, a human IgG1λ mAb that selectively binds to and inhibits CD 73, will be administered following Durvalumab. Please note duvalumab will always be given first. Oleclumab will be given in an outpatient setting at a dose of 3000 mg IV fixed dose over one hour. Pharmaceutical details and preparation are given in section 8.

Durvalumab

Durvalumab, a human IgG1κ mAb directed against PD-L1, and with reduced binding to C1q and the Fcy receptors. It will be given immediately before Oleclumab beginning week 1 at a dose of 1500 mg IV over 1 hour. No premedications are needed. Pharmaceutical details and preparation are given in section 8.

5.1.2.3 Cohort C

Monalizumab is a mAb of the IgG4 subtype that specifically binds and blocks the inhibitory receptor CD94/NKG2A for HLA-E, potentially restoring the ability of peripheral and tumor infiltrating NK cells or cytotoxic CD8+ T-cells to kill HLA-E expressing tumor cells. It will be administered following Durvalumab infusion at a dose of 750mg. Pharmaceutical details and preparation are given in section 8

Durvalumab

Durvalumab will be given immediately following monalizumab beginning week 1 at a dose of 1500 mg IV over 1 hour. No premedications are needed. Pharmaceutical details

and preparation are given in section 8.

5.1.3 Treatment and Follow Up visits

Once enrolled on trial, he/she will have the following visits/events. The study calendar is in section 10 outlines schedule of treatments and assessments. Treatment will not commence until at least 2 weeks from prior systemic chemotherapy. Patients may undergo screening during this time or after two weeks. There is no maximum time from prior chemotherapy till immune-therapy treatment.

PREOPERATIVE SCHEDULE

Refer to Table 10.1 for the preoperative schedule of visits, assessments and treatments for all cohorts.

Note, due to the variation in recovery from surgical resection, weeks will restart following surgical resection when Durvalumab is administered.

POST-OPERATIVE SCHEDULE

Refer to Table 10.2 for cohort A post-operative schedule and Table 10.3 for cohort B and C post-operative schedule.

5.2 General Concomitant Medication and Supportive Care Guidelines

No formal drug interaction studies have been performed with either experimental agent. However, as an antibody, it is not expected to cause significant interaction with medications metabolized by the cytochrome P450 system.

Permitted concomitant medications

Table 5.2.1. Supportive medications

Supportive medication/class of drug:	Usage:
Concomitant medications or treatments (e.g., acetaminophen or diphenhydramine) deemed necessary to provide adequate prophylactic or supportive care, except for those medications identified as “prohibited,” as listed above	To be administered as prescribed by the Investigator
Best supportive care (including antibiotics, nutritional support, correction of metabolic disorders, optimal symptom control, and pain management [including palliative radiotherapy to non-target lesions, etc])	Should be used, when necessary, for all patients
Inactivated viruses, such as those in the influenza vaccine	Permitted

Excluded concomitant medications**Table 5.2.2. Prohibited concomitant medications**

Prohibited medication/class of drug:	Usage:
Any investigational anticancer therapy other than those under investigation in this study	Should not be given concomitantly whilst the patient is on study treatment
mAbs against CTLA-4, PD-1, or PD-L1 other than those under investigation in this study	Should not be given concomitantly whilst the patient is on study treatment
Any concurrent chemotherapy, radiotherapy, immunotherapy, or biologic or hormonal therapy for cancer treatment other than those under investigation in this study	Should not be given concomitantly whilst the patient is on study treatment. (Concurrent use of hormones for non-cancer-related conditions [e.g., insulin for diabetes and hormone replacement therapy] is acceptable. Local treatment of isolated lesions, excluding target lesions, for palliative intent is acceptable [e.g., by local surgery or radiotherapy])

Prohibited medication/class of drug:	Usage:
Immunosuppressive medications including, but not limited to, systemic corticosteroids at doses exceeding <<10 mg/day>> of prednisone or equivalent, methotrexate, azathioprine, and tumor necrosis factor- α blockers	
Should not be given concomitantly, or used for premedication prior to the I-O infusions. The following are allowed exceptions:
 
 • Use of immunosuppressive medications for the management of IP-related AEs, • Use in patients with contrast allergies. • In addition, use of inhaled, topical, and intranasal corticosteroids is permitted. 
A temporary period of steroids will be allowed if clinically indicated and considered to be essential for the management of non-immunotherapy related events experienced by the patient (e.g., chronic obstructive pulmonary disease, radiation, nausea, etc).

Drugs with laxative properties and herbal or natural remedies for constipation	Should be used with caution through to 90 days after the last dose of tremelimumab during the study
Sunitinib	Should not be given concomitantly or through 90 days after the last dose of tremelimumab (acute renal failure has been reported with combination therapy of tremelimumab and sunitinib)
EGFR TKIs	
Should not be given concomitantly.
 
Should be used with caution in the 90 days post last dose of durvalumab.
 
Increased incidences of pneumonitis (with third generation EGFR TKIs) and increased incidence of transaminase increases (with 1st generation EGFR TKIs) has been reported when durvalumab has been given concomitantly.

Live attenuated vaccines	Should not be given through 30 days after the last dose of investigational agents (including SoC)
Herbal and natural remedies which may have immune-modulating effects	Should not be given concomitantly unless agreed by the sponsor

Blood donation

Patients should not donate blood while participating in this study, or for at least 180 days following the last infusion of durvalumab or tremelimumab.

Reproductive Guidelines

The following restrictions apply while the patient is receiving study treatment and for the specified times before and after:

Female patient of child-bearing potential

Females of childbearing potential who are sexually active with a non-sterilized male partner must use at least 1 **highly** effective method of contraception (Table 5.2.3) from the time of screening and must agree to continue using such precautions for 180 days after the last dose of durvalumab + oleclumab or durvalumab + monalizumab combination therapy or 90 days after the last dose of durvalumab monotherapy. Non-sterilized male partners of a female patient must use male condom plus spermicide throughout this period. Cessation of birth control after this point should be discussed with a responsible physician. Not engaging in sexual activity for the total duration of the drug treatment and the drug washout period is an acceptable practice; however, periodic abstinence, the rhythm method, and the withdrawal method are not acceptable methods of birth control. Female patients should also refrain from breastfeeding throughout this period.

Male patients with a female partner of childbearing potential

Non-sterilized males who are sexually active with a female partner of childbearing potential must use a male condom plus spermicide from screening through 180 days after receipt of the final dose of durvalumab + oleclumab or durvalumab + monalizumab combination therapy or 90 days after receipt of the final dose of durvalumab monotherapy. Not engaging in sexual activity is an acceptable practice; however, occasional abstinence, the rhythm method, and the withdrawal method are not acceptable methods of contraception. Male patients should refrain from sperm donation throughout this period.

Female partners (of childbearing potential) of male patients must also use a highly effective method of contraception throughout this period (Table 5.2.3).

Females of childbearing potential are defined as those who are not surgically sterile (i.e., bilateral tubal ligation, bilateral oophorectomy, or complete hysterectomy) or post-menopausal. Women will be considered post-menopausal if they have been amenorrheic for 12 months without an alternative medical cause. The following age-specific requirements apply:

- Women <50 years of age would be considered post-menopausal if they have been amenorrheic for 12 months or more following cessation of exogenous hormonal treatments and if they have luteinizing hormone and follicle-stimulating hormone levels in the post-menopausal range for the institution or underwent surgical sterilization (bilateral oophorectomy or hysterectomy).
- Women ≥50 years of age would be considered post-menopausal if they have been amenorrheic for 12 months or more following cessation of all exogenous hormonal treatments, had radiation-induced menopause with last menses >1 year ago, had chemotherapy-induced menopause with last menses >1 year ago, or underwent surgical sterilization (bilateral oophorectomy, bilateral salpingectomy or hysterectomy).

Highly effective methods of contraception, defined as one that results in a low failure rate (i.e., less than 1% per year) when used consistently and correctly are

described in (Table 5.2.3). Note that some contraception methods are not considered highly effective (e.g., male or female condom with or without spermicide; female cap, diaphragm, or sponge with or without spermicide; non-copper containing intrauterine device; progestogen-only oral hormonal contraceptive pills where inhibition of ovulation is not the primary mode of action [excluding Cerazette/desogestrel which is considered highly effective]; and triphasic combined oral contraceptive pills).

Table 5.2.3. Highly effective methods of contraception (<1% failure rate)

Barrier/Intrauterine methods	Hormonal Methods

 • Copper T intrauterine device • Levonorgestrel-releasing intrauterine system (e.g., Mirena®)^a 	
 • Implants: Etonogestrel-releasing implants: e.g. Implanon® or Norplant® • Intravaginal: Ethinylestradiol/etonogestrel-releasing intravaginal devices: e.g. NuvaRing® • Injection: Medroxyprogesterone injection: e.g. Depo-Provera® • Combined Pill: Normal and low dose combined oral contraceptive pill • Patch: Norelgestromin/ethinylestradiol-releasing transdermal system: e.g. Ortho Evra® • Minipill: Progesterone based oral contraceptive pill using desogestrel: Cerazette® is currently the only highly effective progesterone based pill

^a This is also considered a hormonal method

5.4 Duration of Therapy

In the absence of treatment delays due to adverse events, treatment may continue until one of the following criteria applies:

- X Disease recurrence
- X Intercurrent illness that prevents further administration of treatment,
- X Unacceptable adverse events(s),
- X Patient decides to withdraw from the study, or
- X General or specific changes in the patient's condition render the patient unacceptable for further treatment in the judgment of the investigator.

5.4 Duration of Follow Up

Patients may be followed for up to 2 years from liver surgery or until death, whichever occurs first. Patients removed from study for unacceptable adverse events will be followed until resolution or stabilization of the adverse event.

Note after one year of follow-up without recurrence schedule of follow-ups can be adjusted according to standard of care. This will take precedence over the study calendar.

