5. TREATMENT PLAN

5.1 Study Design and Duration

This study is an open-label, single center trial assessing the safety and feasibility of using perioperative neoadjuvant and adjuvant immune-therapy for resectable liver or lung metastases.

Cohort A will consist of neoadjuvant tremelimumab 75 mg IV flat dose and durvalumab 1500 mg IV flat dose. Adjuvant therapy will consist of 4 monthly doses of durvalumab 1500mg IV.

Cohort B will consist of neoadjuvant oleclumab 3000 mg IV flat dose followed by durvalumab 1500 mg IV flat dose. Adjuvant therapy will consist of 4 months of oleclumab every two weeks at 3000 mg IV flat dose and durvalumab every 4 weeks at 1500 mg IV flat dose. On days oleclumab and durvalumab are both administered, oleclumab will be given first (see Section 8.1.4).

Cohort C will consist of neoadjuvant durvalumab 1500 mg IV flat dose then Monalizumab 750mg IV flat dose. Adjuvant therapy will consist of 4 months of durvalumab 1500 mg IV flat dose and monolizumab 750 mg, both administered every four weeks.

[figure not shown]
Cohort A has been enrolling since the study initiation and will enroll up to 25 patients. At the time of amendment activation initially opening, cohort B may enroll 5 patients followed by 5 patient enrollment for cohort C. Enrollment will continue in this alternating manner with approximately 5 patient blocks at a time for these cohorts. Enrollment may be adjusted based on Medimmune/MD Anderson determined priorities and drug availability. Cohort B and C will each be 15 patients.

[figure not shown]

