12.3 Study Timetable and End of Study

An individual subject will be considered to have completed the study if the subject was followed through the DLT-evaluation period or experienced a DLT during the DLT-evaluation period (for subjects in the dose-exploration phase) or the subject completed at least 1 on-treatment disease evaluation (for subjects in dose-expansion phase) regardless of the number of doses of investigational product that was received. The end of the study ("study completion") is 5 years after the final subject is enrolled or the date the study is closed by the sponsor, whichever occurs first.

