13. STATISTICAL CONSIDERATIONS

13.1 Endpoints

1. Primary Endpoints

- Feasibility will be assessed by whether or not the patient successfully goes to surgery following the planned treatments, scans, and biopsy.
- Safety will be assessed by CTCAE version 4.03 for cohort A and 5.0 for cohorts B and C.

2. Secondary Endpoints

- Various immune parameters
- Response - irRECIST
- Overall survival (OS) measured from the date of study entry until death from any cause
- Relapse-free survival (RFS) from the date of study entry until relapse or death from any cause

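### Follow-up for OS and RFS is undefined for unresected and lung-only patients, and the completion rule in Section 12.3 belongs to a different kind of trial

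*Combined protocol and SAP*

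**What the plan says.** The relevant statements are spread over several sections of the combined protocol and SAP.

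- Section 5.4 (Duration of Follow Up): "Patients may be followed for up to 2 years from liver surgery or until death, whichever occurs first". After one year without recurrence, visits may move to standard of care. The section also says that patients taken off for unacceptable adverse events are followed until the event resolves or stabilises. It says nothing about patients who come off for other reasons.
- Section 12.3: a subject has completed the study if "the subject was followed through the DLT-evaluation period or experienced a DLT during the DLT-evaluation period" (for a dose-exploration phase), or after at least one on-treatment disease evaluation (for a dose-expansion phase). Separately, the end of the study "is 5 years after the final subject is enrolled or the date the study is closed by the sponsor, whichever occurs first".
- Section 5.1: "This study is an open-label, single center trial assessing the safety and feasibility" of perioperative immunotherapy for liver or lung metastases, given at flat doses in three cohorts (25, 15 and 15 patients).
- Section 13.3: a patient not resected within 12 weeks is removed from the trial.
- Tables 10.2 and 10.3: the follow-up calendars, with visits and CT every 4 months. Both are titled as post-resection calendars.
- Section 13.1: "Overall survival (OS) measured from the date of study entry until death from any cause". RFS also runs from study entry there, to relapse or death.
- Section 1.2: RFS is to be estimated in everyone enrolled.
- Section 13.4: OS and RFS are shown by Kaplan-Meier methods. No data cut-off or censoring rule is given, and there is no reference to 5.4 or 12.3.

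**The concern.** OS and RFS are meant to describe the whole enrolled group from study entry, but the follow-up rules are written only for patients who have had liver surgery. Two groups fall outside them.

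Lung-only patients attend the post-resection visits, but no date ends their follow-up. Unresected patients lose more: they have no clock and no calendar, and they are removed at 12 weeks. Section 12.3 would be the natural place to look for a fallback, but its subject-level rule refers to phases and a DLT period that the trial does not define.

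The unresected group is the one that matters for the estimates. Kaplan-Meier methods assume that a censored patient has the same outlook as those still under observation. A patient who missed surgery because the disease progressed does not. Censoring such patients at removal takes poor-prognosis patients out of the risk set and would tend to push both curves upwards. Section 13.4 says the results will be used to design the next trial, so an optimistic curve could be carried forward.

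**Working it through.** The plan gives no event count or power figure that depends on follow-up, so there is nothing of its own to reproduce. The check compares the rules for each type of patient and then counts those affected.

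**Rules by type of patient**

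| Patient | Clock in 5.4 | Follow-up calendar | Subject completion in 12.3 |
|---|---|---|---|
| Liver resection | 2 years from surgery | Tables 10.2, 10.3 | refers to phases that do not exist here |
| Lung resection only | none | Tables 10.2, 10.3 | same |
| Not resected | none; removed at 12 weeks (13.3) | none | same |

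**Observation time from first dose.** I take the 12 weeks in 13.3 to run from first dose; the sentence is incomplete on this. Section 5.1 and Table 10.1 give 3 to 10 weeks for resection, and these passages need reconciling.

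- Liver-resected patient: 24 months plus time to surgery. Surgery at week 3 gives 24 + 21/30.4375 = 24.7 months. Surgery at week 12 gives 24 + 84/30.4375 = 26.8 months.
- Unresected patient: 84/30.4375 = 2.8 months. The 90-day safety window after the last dose (Sections 7.5 and 7.6.1.2) extends this to 90/30.4375 = 3.0 months, only 6 days more.

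**How many patients.** The number unresected is N × (1 − surgery rate).

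- At the planning rate of 80% (Section 13.2): 25 × 0.20 = 5 in cohort A and 15 × 0.20 = 3 in each of B and C, so 11 of 55.
- At 60%, the feasibility floor in Section 13.4: 10 + 6 + 6 = 22 of 55.
- Observed so far (Section 2.6): of 14 patients who reached the point of surgery, 11 were resected and 3 (21%) were not. Two of the three had progressed; the third had liver toxicity from earlier chemotherapy.

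The number of lung-only patients cannot be derived from the documents.

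**Direction and possible size, using those 14 patients.** Suppose no one else has relapsed or died by the time of removal, and the third unresected patient is still at risk.

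- If the two progressors count as RFS events, the estimate at that point is 1 − 2/14 = 0.857.
- If they are censored at removal, it stays at 1.00.
- From then on both curves are multiplied by the same factors, so the second stays 14/12 = 1.17 times the first.

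This is an illustration from 14 patients. It assumes that progression before surgery counts as an RFS event, which the plan does not say. Section 11.1.5 starts RFS at surgery, so an unresected patient has no origin under that definition, whereas Section 13.1 starts it at study entry. For OS no such question arises: a death after about 3 months in an unresected patient would not be collected under the rules as written.

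**The case against.** A reader might infer that follow-up ends at three conflicting points, so that OS and RFS are cut differently depending on the section used. The documents do not support that. The 2 years in 5.4 is a permissive limit for each patient. The 5 years in 12.3 is a ceiling for the whole study, with sponsor closure as an alternative. Follow-up of 24.7 to 26.8 months after first dose fits inside 60 months after the last enrolment, so both can be met. No section sets a data cut for OS or RFS.

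A reader might also infer that 12.3 closes a patient's follow-up at the scan before surgery. It does not. The sentence defines a completion status, censors nobody, and applies only to subjects in phases that this trial lacks. Nor is it an error that 2 years falls short of the 3-year PFS and 5-year OS figures in the background section. Those are context, and no such landmark is planned.

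On what remains, the best reply is that this is leftover wording with little effect. A lung-only patient is still bounded by the study end in 12.3, so nothing is truncated for that group. OS and RFS are secondary, no formal hypothesis is tested, and sample size and stopping rules do not use them. A single centre may well track survival from its own records after a patient leaves the trial.

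Most of that stands, and it limits the weight of the point. It does not answer the unresected group. The protocol asks for no status collection on them after removal, and it follows patients who left for only one other reason, adverse events. Whether the site would track them anyway cannot be told from the documents.

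**Conclusion.** The point holds as a gap in coverage. Section 12.3 contains no usable rule for when a subject completes this trial. Section 5.4 gives lung-only patients no clock. Unresected patients, about 11 of 55 on the planning assumption, are removed at 12 weeks with no further follow-up specified, although both time-to-event endpoints are meant to include them.

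Followed as written, the Kaplan-Meier estimates of OS and RFS could be too favourable, including at times before 2 years. That rests on three assumptions: removal under 13.3 ends data collection; these patients are censored at that point; and those unresected because of progression have a worse outlook than the rest. The direction is plausible. The documents do not allow the size to be estimated beyond the counts and the 14-patient illustration.

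The primary feasibility and safety assessments are not affected. The text should be corrected because the change is cheap and the curves will inform the next trial.

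**What to change.** 1. In Section 5.4 (Duration of Follow Up), replace 'liver surgery' with 'metastasectomy (liver or lung), or first dose if not resected'. Add that relapse and survival status are collected by chart or telephone for every dosed patient, including those not resected or removed under 13.3, until death, withdrawal of consent or one stated follow-up horizon. Keep the existing allowance to move to standard-of-care visits after one recurrence-free year.
2. In Section 12.3, replace the DLT and dose-expansion sentence with: 'A subject completes the study at death or at the end of the follow-up in 5.4.' The study-level end date can stay.
3. If the 2-year limit is kept, report Kaplan-Meier estimates of OS and RFS only to about 24 months. With change 1, resected patients are covered to 24.7 months or more after first dose and unresected patients to 24 months, so that is the common horizon.

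The two RFS definitions (11.1.5 and 13.1) should be aligned in the same amendment, with a statement of whether progression before surgery counts as an event. The status data collected under change 1 serve either definition.

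The cost is protocol wording plus periodic status checks on patients who no longer attend. No additional scans, clinic visits or patients are needed.
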